In collaboration with Drs. [name] and [name], we will perform flow cytometry-based analysis of peripheral-blood mononuclear cells to evaluate for (1) T cell subsets and expression of inhibitory immune receptors on different immune cells, (2) quantification of circulating CD4/CD8 populations, and (3) levels of circulating regulatory T cells and tumor reactive lymphocytes (collaboration with [name] and Drs. [name]/[name]). Peripheral blood samples will be analyzed by FACS-gating to determine the percentage of activated effector cells (using CD4/CD25+ fraction and CD69 expression) and regulatory T cells (measuring expression of Foxp3, GITR, CTLA-4, CD127, and CD62L on the CD4/CD25+ population). We will then stain for CD45RA to evaluate for the naive memory cell prevalence and CD45RO, CCR7 and CD28 for memory cell response. We will evaluate if *ex vivo* immunologic response correlates with levels of memory effector and regulatory T cells. We will evaluate the immunomodulatory effect of decitabine alone and in conjunction with checkpoint blockade in AML by evaluating for (1) transcriptional induction of and (2) binding to leukemia-associated antigens as suggestion of

enhanced presentation of leukemia antigens to T cells. We will evaluate if decitabine enhances antigen presentation. There is preclinical evidence that HMA therapy enhances MHC class I and co-stimulatory molecule expression which may increase recognition of leukemia-associated antigens (LAA). We will use real-time quantitative polymerase chain reaction to measure leukemia-associated antigens such as WT1, MUC1, and PR3, which may be targets for AML immunotherapy. In collaboration with Drs. [name]/[name], we will evaluate the percentage of CD8+ T cells binding tetramers constructed from these antigens and for functional activity in the tetramer-positive population by measuring corresponding levels of IFN-gamma, granzyme, IL-4, and IL-10 expression by FACS staining.

-Sample type: aspirate and peripheral blood

-Time-points for collection: baseline (screening), end of the lead in, and end of cycle 2.

-Correlative to be performed in:

[name] laboratory at Beth Israel Deaconess Medical Center

Address: [name]

-Total anticipated # samples: up to 3 per patient

10. STUDY CALENDAR

10.1 Study Schedule

Baseline evaluations and screening labs/procedures performed are to be conducted within 2 weeks prior to start of protocol therapy except for serum pregnancy in women of childbearing potential which must be repeated if resulted > 72 hours prior to treatment start. Baseline evaluation can be used as screening for eligibility if performed within 1 week of starting protocol therapy. If treatment start occurs within 48 hours of registration, then baseline evaluation does NOT need to be repeated to confirm eligibility. Scans, EKG and echocardiogram (or MUGA scan) are allowed within 4 weeks of treatment start (day 1 of the lead in period). In the event that the patient's condition is deteriorating, laboratory evaluations should be repeated within 48 hours prior to initiation of the next cycle of therapy. Please see screening table below for specific windows for diagnostic tests including bone marrow and PET.

Screening, Priming and Induction Period												
	Pre-Study	Lead In D1	Lead In D15 ^b	Lead In D24 ^a	C1 D1 ^b	C1 D15 ^b	C1 D24 ^a	C2 D1 ^b	C2 D24 ^a	C3 D1 ^b	C4 D1 ^b	C4 D24 ^a
Ipilimumab^A					X			X		X	X	
Decitabine^B		X			X			X		X	X	
Informed consent	X											
Demographics	X											
Medical history	X											
Concurrent meds	X	X	X		X	X		X		X	X	
Physical Exam	X	X	X		X	X		X		X	X	
Vital signs	X	X	X		X	X		X		X	X	
Height	X											
Weight	X	X			X			X		X	X	
Performance status	X				X			X				X
CBC w/diff, plts	X	X	X	X	X	X	X	X	X	X	X	X
Serum chemistry^c	X	X	X		X	X		X		X	X	
Immune-related labs^d	X				X							X
Adverse event evaluation^{e,q,r}	X		X		X	X		X		X	X	
GVHD Assessment	X				X			X		X	X	
PET^f	X ^f								X ^f			X ^g
B-HCG^h	X ^h											
Bone marrowⁱ	X			X ^j			X ⁱ		X ⁱ			X ⁱ
Skin biopsy^k	X ^k						X ^k		X ^k			X ^k
T cell chimerism^l	X			X			X		X			X
Hepatitis Panel^m	X											
HIV testingⁿ	X											
Echocardiogram^{o,q,s}	X											
EKG^{o,q}	X											
Correlative studies^p	X			X			X		X			X

A: Ipilimumab: Dose as assigned by dose level. Administered every 4 weeks. Dosed per weight on day 1 of a cycle.

B: Decitabine: 20 mg/m2 daily IV for 5 consecutive days on days 1-5. Dosed per weight on day 1 of the lead in period

a: Can be done any time between day 24-28

b: +/- 3 days. If there is evidence of persistent disease or blood counts meet criteria to treat, final bone marrow results are not required prior to dosing on day 1 of next cycle.

c: Albumin, alkaline phosphatase, total bilirubin, bicarbonate, BUN, calcium, chloride, creatinine, glucose, potassium, total protein, SGOT [AST], SGPT [ALT], sodium, uric acid, magnesium, phosphorus.

d: Every 3 months unless clinically indicated: gamma-GT, direct bilirubin, LDH, TSH, and lipase

e: Please see [Appendix F](#) for helpful study check list including immune related AE evaluation

f: PET scans are required only for those with sole extramedullary disease (no marrow involvement by morphology) and optional for those with extramedullary and marrow involved AML. PET scans are standard imaging tests for those with extramedullary disease involvement. Study can be performed any time between day 24-28 at the end of cycles 2 and 4 (suggested time frame). However as clinical scenario may vary with patients with sole extramedullary disease, we will allow imaging window of +/- 4 weeks based on clinical scenario or scheduling logistics. Please send report and imaging (on CD) with redacted PHI for central review of extramedullary AML events to Attn: [name], Research Project Manager for CTEP 10026; Dana-Farber Cancer Institute; [name]. If there are reports only, please fax to [contact] or email to: [contact]

g: If patient has sole extramedullary disease and there was no resolution of FDG-avid disease by the end of cycle 2, then patients should have a repeat PET at the end of cycle 4 per standard of care. Study can be performed any time between day 24-28 at the end of cycles 2 and 4 (suggested time frame). However as clinical scenario may vary with patients with sole extramedullary disease, we will allow imaging window of +/- 4 weeks based on clinical scenario or scheduling logistics. Please send report and imaging (on CD) with redacted PHI for central review of extramedullary AML events to Attn: [name], Research Project Manager for

CTEP 10026; Dana-Farber Cancer Institute; [name]. If there are reports only, please fax to [contact] or email to: [contact]

- h: Serum pregnancy test (women of childbearing potential).- Negative results required within 72 hours of treatment start
- i: For bone marrow biopsies, the minimum requested includes (1) aspirate (if aspirable), (2) core, (3) flow cytometry (if sufficient blasts; may not be possible in setting of low blasts or remission; if MRD flow cytometry is an option we will accept this data in lieu of standard flow cytometry if this test is available at the time of suspected remission), (4) cytogenetics if possible, (5) molecular testing per institutional guidelines (suggested at minimum at time of screening and relapse but not required; correlatives will include genotyping leukemic blasts). Core biopsy is mandatory at screening, at the end of cycles 2 and 4- See sample collection table in section 10.2 for details. If a diagnostic bone marrow biopsy was performed within 4 weeks of treatment start and no anti-leukemic therapy has been given (except for hydrea and radiation), then flow cytometry and cytogenetics do not need to be repeated. If a diagnostic bone marrow was performed within 2 weeks of treatment start, then only a research aspirate and research core are required to be collected during screening. In cases of persistent leukemic blood, bone marrow biopsy can be performed on day 1 of subsequent cycle prior to treatment.
- j: Aspirate ONLY for correlative study (unless inaspirable). See Correlative studies.
- k: For those with leukemia cutis only - repeat evaluation at end of cycles 1, 2 and/or 4 (pending response)- If there is suspected resolution or response based on skin exam, biopsy may occur sooner as clinically indicated. After confirmation of resolution of lesion, there does not need to be a repeat biopsy at the same site. If there is concern for persistence of disease based on skin examination, then repeat biopsy is recommended at the end of cycles 1, 2 and/or 4 if it can be safely performed.
- l: Routine response evaluation for patients in Arm A who are status post allo-HCT only. Peripheral blood source only. Can be performed locally and if not available locally then should be analyzed at site where patient's transplant was performed.
- m: For those with known HBV they should get an HBV viral load (PCR). For those with known HCV they should get an HCV viral load (PCR). It is recommended that patients with known HBV get monthly (+/- 14 days) HBV viral load assessments after ipilimumab is initiated. Please update overall PI if there is significant or clinical concern for HBV re-activation despite anti-viral therapy.
- n: For those with known HIV they must get a CD4 count and an HIV viral load (PCR).
- o: Baseline echocardiogram and EKG required for screening (if done within 4 weeks of treatment start does not need to repeat unless there is a clinical concern) and at any other time that is clinically indicated during the trial as it relates to footnote q
- p: Peripheral blood, aspirate, core biopsy, or FFPE to be collected per schedule described correlative table below.
- q: Alert PI if there is concern for cardiac toxicity (minimum assessment: cardiology consult, EKG, echocardiogram, and labs CPK and troponin; refer to section 6.4.7)
- r: Please see section 7.3.5 of the protocol for reporting requirements for GVHD and suspected immune related AEs to enable central review
- s: MUGA scan is a suitable alternative to an echocardiogram
- t: For participants enrolled on Arm A (post transplant), a formal GVHD assessment is required at minimum on Day 1 of each cycle utilizing the GVHD assessment worksheet provided in Appendix B

	Maintenance cycles and end of study										
	C5 D1 ^b	C6 D1 ^b	C7 D1 ^b	C7 D24 ^a	C8 D1 ^b	C9 D1 ^b	C10 D1 ^b	C10 D24 ^a	C11 D1 ^b	C12 D1 ^b	End of study ^{i,j}
Ipilimumab^A	X		X			X			X		
Decitabine^B	X	X	X		X	X	X		X	X	
Concurrent meds	X	X	X		X	X	X		X	X	
Physical Exam	X	X	X		X	X	X		X	X	X ^k
Vital signs	X	X	X		X	X	X		X	X	
Height	X										
Weight	X	X	X		X	X	X		X	X	
Performance status	X	X	X		X	X	X		X	X	
CBC w/diff, plts	X	X	X	X	X	X	X	X	X	X	X
Serum chemistry^c	X	X	X		X	X	X		X	X	X
Immune-related labs^d			X				X				X
Adverse event evaluation^{e,f,m}	X	X	X		X	X	X		X	X	X ^k
GVHD Assessment	X	X	X		X	X	X		X	X	X
Bone marrow^f				X ^f				X			X ^f
T cell chimerism^g											X
Correlative studies^h				X				X			X

A: Ipilimumab: Dose as assigned by dose level. Administered every 8 weeks. Dosed per weight on day 1 of a cycle.
B: Decitabine: 20 mg/m² daily IV for 5 consecutive days on days 1-5. Dosed per weight on day 1 of the lead in
a: Can be done any time between day 24-28
b: +/- 3 days
c: Albumin, alkaline phosphatase, total bilirubin, bicarbonate, BUN, calcium, chloride, creatinine, glucose, potassium, total protein, SGOT [AST], SGPT [ALT], sodium, uric acid, magnesium, phosphorus.
d: At baseline, C1D1, and then every 3 cycles thereafter or more frequently when clinically indicated: gamma-GT, direct bilirubin, LDH, TSH, and lipase
e: Please see [Appendix F](#) for helpful study check list including immune related AE evaluation
f: For bone marrow biopsies, the minimum requested includes (1) aspirate (if aspirable), (2) core, (3) flow cytometry (if sufficient blasts; may not be possible in setting of low blasts or remission; if MRD flow cytometry is an option we will accept this data in lieu of standard flow cytometry if this test is available at the time of suspected remission), (4) cytogenetics if possible, (5) molecular testing per institutional guidelines (suggested at minimum at time of screening and relapse; but not required correlates will include genotyping leukemic blasts). If concern for relapse after a response is achieved, patient should get marrow per routine clinical standards. At the end of treatment (either completion of therapy or at time of suspected relapse), encourage marrow sampling unless clinical condition precludes this. In cases of persistent leukemic blood, bone marrow biopsy can be performed on day 1 of subsequent cycle prior to treatment.
g: Routine response evaluation for patients in Arm A who are status post allo-HCT only. Peripheral blood source. Can be performed locally and if not available locally then should be analyzed at site where patient's transplant was performed.
h: Peripheral blood, aspirate, core biopsy, or FFPE to be collected per schedule described correlative table below.
i: End of study includes patients who: complete 12 combination cycles, come off study for toxicity, or have disease progression.
j: Quarterly phone call for survival follow-up for up to 1 year after treatment is complete. All efforts to contact the patient should be made.
k: As there can be a delay in the presentation of an immune-related adverse event, patients will be asked to come back for a clinical exam 3 months (+/-1 month) after their last treatment on study.
l: Alert PI if there is concern for cardiac toxicity (minimum assessment: cardiology consult, EKG, echocardiogram, and labs CPK and troponin; refer to section 6.4.7)
m: Please see section 7.3.5 of the protocol for reporting requirements for GVHD and suspected immune related AEs to enable central review
n: For participants enrolled on Arm A (post transplant), a formal GVHD assessment is required at minimum on Day 1 of each cycle utilizing the GVHD assessment worksheet provided in Appendix B

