5.1.2 Decitabine

Administration: Per institutional guidelines.. Patients will be dosed for 5 consecutive days unless there is a clinical reason to hold the drug as described in section 6 of the protocol

Dosing: On days when both drugs are required, decitabine should be administered prior to ipilimumab. Treatment doses of both decitabine and ipilimumab will be based on the participant's weight obtained on day 1 of each cycle.

Prophylaxis: No prophylaxis is required however anti-viral therapy (i.e. acyclovir 400 mg po three times a day or equivalent) is common practice.

Supportive care regimens: Prior to administration of chemotherapy (decitabine) recommend an anti-emetic agent to be given 30 minutes (+/- 15 minutes) prior to chemotherapy to increase tolerability. Anti-emetic agent should be per institutional guidelines.

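### Sections 5.1.1 and 5.1.2 and footnote B of both study calendars give conflicting weight rules for decitabine, so the dose can differ from cycle 1 onward if weight changes

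*Combined protocol and SAP*

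**What the plan says.** Sections 5.1.1 (ipilimumab) and 5.1.2 (decitabine) carry the same sentence: "Treatment doses of both decitabine and ipilimumab will be based on the participant's weight obtained on day 1 of each cycle". It names both drugs and makes no exception.

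The two calendars in section 10.1 separate the drugs. In both, footnote A covers ipilimumab and reads "Dosed per weight on day 1 of a cycle", which agrees with section 5.1. Footnote B covers decitabine. In the priming and induction calendar it gives the dose as "Decitabine: 20 mg/m2 daily IV for 5 consecutive days on days 1-5" and continues "Dosed per weight on day 1 of the lead in period". In the maintenance calendar, which covers cycles 5 to 12, it gives the same dose and continues "Dosed per weight on day 1 of the lead in".

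Both calendars schedule a weight on day 1 of every cycle, including the cycles in which only decitabine is given. Height is scheduled before the study and again on day 1 of cycle 5. The protocol names no body-surface formula, sets no weight-change threshold for recalculating a dose, and does not say whether the treatment section or the calendar takes precedence.

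**The concern.** Once weight has changed since the lead-in, the two instructions cannot both be followed. A site working from section 5.1 would recalculate the decitabine dose each cycle. A site working from footnote B would carry the lead-in weight forward. Each would depart from the other text, and because the measurements for either rule are already on the schedule, the divergence could go unnoticed.

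Decitabine is the fixed component of the combination: section 5.1 states that it is not escalated, and the primary objective is an MTD or RP2D for the combination in each arm, from three to six patients per dose level. Section 5.2 also asks investigators to separate toxicity of the combination from toxicity of decitabine alone. A decitabine dose that depends on which page was read adds avoidable variation to that judgement. Weight change is foreseeable: section 5.2 lists weight loss among the DLT exceptions, and the section 7.1 risk lists include weight loss for ipilimumab and anorexia for both drugs.

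**Working it through.** **Text comparison**

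| Place | Drug | Weight used |
|---|---|---|
| Sections 5.1.1 and 5.1.2 | Both | Day 1 of each cycle |
| Section 10.1, both calendars, footnote A | Ipilimumab | Day 1 of a cycle |
| Section 10.1, priming and induction, footnote B | Decitabine | Day 1 of the lead-in |
| Section 10.1, maintenance, footnote B | Decitabine | Day 1 of the lead-in |

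Ipilimumab is consistent throughout; decitabine is not. Footnote B cannot be read as covering only the first decitabine course, because the maintenance calendar starts at cycle 5 and has no lead-in column. There it can only mean that the lead-in weight is carried forward.

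**When the rules can differ**

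- Lead-in cycle: both rules use the same weight, so the difference is 0.
- Cycles 1 to 12: a difference is possible if weight has changed, so up to 12 planned cycles are exposed, plus any additional maintenance allowed at the end of section 5.1.
- DLT window: 56 days from day 1 of cycle 1. With 28-day cycles given on schedule, only the decitabine courses of cycles 1 and 2 fall inside it. These start 28 and 56 days after lead-in day 1, so the relevant weight change is over roughly 4 to 8 weeks.

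**Size**

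The plan has no figure to reproduce here. The one input from the documents is the dose of 20 mg/m² daily for 5 days. The body-surface formulas, the example patient (170 cm, 80 kg at lead-in) and the weight changes are assumptions.

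Mosteller: BSA = √(height in cm × weight in kg / 3600). With height fixed, current-weight dose ÷ lead-in-weight dose = √(1 + c), where c is the proportional weight change. Du Bois: BSA is proportional to weight^0.425, so the ratio is (1 + c)^0.425.

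The lead-in-weight dose for the example patient is 20 × √(170 × 80 / 3600) = 20 × 1.944 = 38.87 mg/day.

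| Weight change c | √(1 + c) | Current-weight dose vs lead-in-weight dose, Mosteller | Du Bois |
|---|---|---|---|
| −20% | 0.894 | −10.6% | −9.0% |
| −10% | 0.949 | −5.1% | −4.4% |
| −5% | 0.975 | −2.5% | −2.2% |
| 0 | 1 | 0 | 0 |
| +5% | 1.025 | +2.5% | +2.1% |
| +10% | 1.049 | +4.9% | +4.1% |
| +20% | 1.095 | +9.5% | +8.1% |

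In milligrams, a 10% loss takes the Mosteller dose from 38.87 to 36.88 mg/day, a difference of about 10.0 mg over a 5-day course (8.4 mg by Du Bois).

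**The case against.** The strongest reply is that this is a drafting inconsistency with little consequence. Ipilimumab is the escalated drug and its weight rule is the same everywhere. Because decitabine is dosed by surface area, its dose moves by only about half as much as weight. Only two decitabine courses fall inside the DLT window on schedule. No sample size, probability or decision rule depends on the point. All of this stands, and it is why the point is minor.

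It might also be said that section 5.1.2 defers to institutional guidelines. That deferral concerns administration; the same section states the dosing-weight rule separately, so the conflict remains.

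A reader might infer more than the documents support:

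- That every patient's dose depends on the passage followed. It does not: the rules coincide in the lead-in and in any cycle where weight is unchanged.
- That sites dose from the calendars, or that exposure will differ between sites. The documents do not say which text sites use. Divergence is possible, not shown.
- That the MTD or RP2D would be biased. The documents give no expected weight change and no basis for a direction of effect, and the time from lead-in to the last course in the DLT window is short.

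**Conclusion.** There is an internal contradiction in current operative text about the weight used to dose decitabine, and no reading of the two calendars removes it. It matters only from cycle 1 onward and only if weight changes. Over assumed changes of 5% to 20% in either direction, the discrepancy runs from about 2.5% to about 10% of the decitabine dose by the square-root formula, slightly less by Du Bois. The documents do not indicate how common such changes would be. The effect on dose-escalation decisions is probably small; the larger discrepancies are more plausible late in maintenance, when more time has passed since the lead-in. This is worth correcting as a minor point. The documents do not show which rule was intended, and this review takes no position on that.

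**What to change.** Reconcile sections 5.1.1 and 5.1.2 with footnote B of both calendars in section 10.1, so that all four places state one decitabine weight rule. The choice of rule belongs to the sponsor. The cost is a phrase in two footnotes or in two sections. The weights needed for either rule are already scheduled on day 1 of each cycle, so there is no added visit, measurement or analysis.

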10.2 Correlative Sample Schedule

All sites will send samples to Dana-Farber Cancer Institute at the following address:

Dana-Farber Cancer Institute
 Smith Receiving
 Pasquarello Tissue Bank- CMCF
 [name]
 [name]

Time Point ¹	Sample Type To Collect ¹	Sample Tube/Container ² , Amount Requested (Proposed Processing Site ³)	Shipping Method ^{4,5}	Shipping Address	
Screening or pre-treatment (T0)	Marrow Aspirate	1 x 10 mL green top (P) 1 x 5 mL green top (A)	FedEx Priority overnight with cool pack ⁴	Dana-Farber Cancer Institute	
	Marrow Aspirate	2 mL lavender top (C)			
	Peripheral blood ¹⁰	4 x 10 mL lavender top (P) 1x 10mL green top (A)			
	Extramedullary FFPE Tissue Block ⁵	No specific size; standard paraffin blocks or unstained glass slides (R)	FedEx Priority overnight or same day RT		
	(Mandatory) Bone Marrow Core ⁹	No specific size; 10% buffered formalin			
End ⁸ of Lead-In (T1)	Marrow Aspirate ⁷	1 x 10 mL green top (P)	FedEx Priority overnight with cool pack ⁴	Dana-Farber Cancer Institute	
	Peripheral blood	3 x 10 mL lavender top (P) 1x 10 mL green top (A)			
End ⁸ of Cycle 1 ¹² (T2)	Marrow Aspirate	1 x 10 mL green top (P)	FedEx Priority overnight with cool pack ⁴	Dana-Farber Cancer Institute	
	Marrow Core	5-8 Unstained Slides			
	Peripheral Blood	4 x 10 mL lavender top (P)			
	Extramedullary FFPE Tissue Block ⁵	No specific size; standard paraffin blocks or unstained glass slides (R)	FedEx Priority overnight or same day RT		
End ⁸ of Cycle 2 ¹² (T3)	Marrow Aspirate	1 x 10 mL green top (P) 1 x 5 mL green top (A)	FedEx Priority overnight with cool pack ⁴	Dana-Farber Cancer Institute	
	Peripheral Blood ¹⁰	4 x 10 mL lavender top (P) 1x 10 mL green top (A)			
	Extramedullary FFPE Tissue Block ⁵	No specific size; standard paraffin blocks or unstained glass slides (R)	FedEx Priority overnight or same day RT		
	(Mandatory) Bone Marrow Core ⁹	No specific size; 10% buffered formalin (R)			
End ⁸ of Cycle 4 ¹²	Marrow Aspirate	1 x 10 mL green top (P)	FedEx Priority overnight with	Dana-Farber Cancer Institute	

(T4)	Marrow Aspirate ⁶	2 mL lavender top (C)	cool pack ⁴		
	Peripheral Blood	3 x10 mL lavender top (P)			
	Extramedullary FFPE Tissue Block ⁵	No specific size; standard paraffin blocks or unstained glass slides (R)	FedEx Priority overnight or same day RT		
	(Mandatory) Bone Marrow Core ⁹	No specific size; 10% buffered formalin			
End ⁸ of Cycle 7 (T5)	Marrow Aspirate	1 x 5 mL green top (P)	FedEx Priority overnight with cool pack ⁴	Dana-Farber Cancer Institute	
	Peripheral Blood	2 x 10 mL lavender top (P)			
End ⁸ of Cycle 10 (T6)	Marrow Aspirate	1 x 5 mL green top (P)	FedEx Priority overnight with cool pack ⁴	Dana-Farber Cancer Institute	
	Peripheral Blood	2 x 10 mL lavender top (P)			
End of Treatment or Suspected Relapse (T7) ¹²	Marrow Aspirate	1 x 5 mL green top (P)	FedEx Priority overnight with cool pack ⁴	Dana-Farber Cancer Institute	
	Marrow Aspirate ⁶	2 mL lavender top (C)			
	Peripheral Blood	2 x 10 mL lavender top (P)			
	Extramedullary FFPE Tissue Block ⁵	No specific size; standard paraffin blocks or unstained glass slides (R)	FedEx Priority overnight or same day RT		
	(Optional) Bone Marrow Core ⁹	No specific size; 10% buffered formalin			
Clinically indicated (unscheduled) (Tx)	Marrow Aspirate	1 x 5 mL green top (P)	FedEx Priority overnight with cool pack ⁴	Dana-Farber Cancer Institute	
	Peripheral Blood	2 x 10 mL lavender top (P)			
One-time for germline DNA assessment ¹¹ (Optional)	Skin biopsy	Punch 4 mm in sterile container with saline.	Fed Ex Priority overnight Frozen	Dana-Farber Cancer Institute	
Suspected Ipi-induced Toxicity (Optional) ¹³	Skin biopsy	Punch 4 mm in sterile container with saline.	Fed Ex Priority overnight Frozen	Dana-Farber Cancer Institute	

¹All efforts should be made to collect correlative samples unless there are unforeseen clinical circumstances, or patient refusal.

²**Containers/Tubes:** Green top= **sodium heparin** tube; Lavender top = EDTA tube. Any tube size combination is acceptable to collect the approximate requested volume of blood or aspirate, however please use what is included in kits if possible to reduce missed samples.

³**Proposed Processing +/- Storage Sites for samples:** **(P) Pasquarello Heme Tissue Bank Lab** (Dana-Farber Cancer Institute, Pasquarello Tissue Bank - J614, Smith Receiving, [name]); **(R) [name] Laboratory**, Attn: [name]/[name], [name], Brigham & Women's Hospital, [name]; **(A) [name] Laboratory (Beth Israel Deaconess Medical Center)**, [name]; **(C) Center for Advanced Molecular Diagnostics**, [name]

⁴**Shipping:** Aspirate and peripheral blood should be shipped with a cool pack if coming overnight (FedEx) and received Monday-Thursday ONLY for processing. Samples coming from participants at the corresponding organization (site: Dana-Farber Cancer Institute) must be submitted before 4 pm Monday-Friday.

⁵**FFPE Tissue Block** (including extramedullary disease biopsies including but not limited to leukemia cutis): At the screening time point, FFPE of extramedullary sites are required for patients enrolling with extramedullary AML only and optional for those enrolling with extramedullary plus marrow involved AML. FFPE samples at screening may be archival (if performed within 12 weeks, then biopsy does not need to be repeated unless a patient received anti-leukemic treatment (such as chemotherapy or radiation) after the biopsy with the exception of hydrea). These extramedullary FFPE tissue block samples can be shipped Monday-Friday at room temperature. These samples do NOT need to be sent with the kit (peripheral blood and aspirate) unless immediately ready; may be sent separately.

⁶**Rapid Heme Panel Sample:** This 1cc aspirate sample will only be collected for all patients in both Arm A and Arm B to perform research-based molecular testing with a Rapid Heme Panel (RHP) (performed in Center for Advanced Molecular

Diagnostics at the Brigham & Women's Hospital, Boston, MA). If a patient has a dry aspirate, then RHP may be drawn from peripheral blood if there are circulating blasts in setting of AML (circulating blasts are not required for a peripheral blood draw in setting of MDS). However, prefer sample to come from aspirate to allow for proper intra-patient and inter-patient comparison. In the event the "end of treatment" time point falls within the first 3 months on study treatment (+/- 2 weeks), this sample is optional.

⁷End of lead-in marrow aspirate sample: This is a research aspirate only; no formal submission for pathology review is required.

⁸End of cycle samples: can be collected any time between Days 24-28.

⁹Bone Marrow Core: At the screening time point, submission of bone marrow biopsy core will be mandatory (to be fixed in 10% buffered formalin prior to sending using materials provided in kit) (this extra core should be collected at time of screening marrow for the purpose of IHC correlative studies). Mandatory submission of bone marrow biopsy core or 6-8 unstained slides will be collected at the end of cycles 1, 2 and 4. For the end of treatment/suspected relapse timepoint, a core is requested, but not mandatory. At the EOT/suspected relapse timepoint, 6-8 unstained slides may be sent in lieu of a fresh core sample. Cores arriving in formalin will be transferred to 70% ethanol and decalcified in the Brigham & Women's Hospital Pathology Core laboratory in preparation for staining with IHC in the [name] Laboratory. These bone marrow core samples should be shipped Monday-Thursday at room temperature. Archival tissue (FFPE) from participants who are consented on the clinical trial including bone marrow biopsies (tissue blocks or slides) performed at other time points where a bone marrow is clinically indicated (while on study) may be requested at a later time for IHC analysis in the [name] laboratory

¹⁰ PB sample for PD studies: It is preferred that the PB is drawn at one visit. However, depending on scenario, the peripheral blood PD sample can be collected over two visits if clinically necessary (e.g. for the "screening/pre-treatment" collection, PB can be collected at screening up until day 1 of lead-in cycle as long as it's prior to decitabine dosing; for the "end of cycle 2" collection, PB can be collected on days 24-28 of cycle 2 up until day 1 of cycle 3 as long as it's prior to decitabine and ipilimumab dosing). If this is the case, please update the study team to anticipate and plan on two sample deliveries.

¹¹Germline assessment: Skin biopsies will be performed on patients who are identified to be exceptional responders (at any point of the trial) and some non-responders (in dose expansion cohort) after discussion with the overall PI. Samples are to be sent in normal saline in appropriate leakproof container to BWH CAMD by way of Dana-Farber. If sent from outside of DFCI, the sample should be sent frozen (both saline and tissue) and shipped to the Pasquarello Tissue Bank at Dana-Farber Cancer Institute. DNA will be extracted in batches in Brigham and Women's Hospital CAMD. This is optional.

¹²FFPE bone marrow core slide or tissue block may be requested if sample available for IHC comparison at this time point.

¹³ Optional, if sample is being taken for clinical reasons, and it is safe to do so, we are requesting a small sample be sent to Dana-Farber Cancer Institute for analysis.

